### **10.3 Shipping Instructions**

All samples will be shipped in compliance with the International Air Transport Association (IATA) Dangerous Goods Regulations. Kits with pre-printed Fed-Ex billing labels will be provided to each participating institution. For E.O. Osepdal Galliera, the supply required for the study will be obtained locally and not provided by CP lab. The samples will be shipped in batches of 4 participants.

#### **10.3.1 Methods for shipping tissue**

Tissue Samples are shipped (Monday-Thursday) for next day delivery to the Biorepository lab at the University of Minnesota. Tissue samples will not be shipped the day before major university holidays.

#### **10.3.2. Methods for shipping the plasma pharmacokinetics samples:**

Once the patient has completed the study, ship the carton containing the pharmacokinetic samples for one patient to the address below. If multiple patients are completing the study, samples from multiple patients can be combined in one shipment. Please note this address is for the pharmacokinetic samples ONLY. Tissue samples should be sent to the address above at UMN.

CP Laboratory  
University of Wisconsin Hospital and Clinics  
[name]  
[name]  
[name]

Call the CP Laboratory to inform them of a shipment [contact] or email the CP Laboratory mailing list [[contact]](mailto:[contact])

Use the express courier service indicated by the shipping label contained in the kit. Closely follow all special shipping instructions outlined in the kit instruction packet.

Ship the PK samples only on Monday, Tuesday or Wednesday to ensure safe arrival during the week. Do not ship the day before a holiday.

Fill the styrofoam cooler with dry ice and put all of the blood samples into the cooler. Place the cooler into the shipping box in which you received the kit.

## **10.4 Tissue Banking**

Biologic specimens collected during the conduct of each clinical trial that are not used during the course of the study will be considered deliverables under the contract and thus the property of the NCI. At study completion, NCI reserves the option to either retain or relinquish ownership of the unused biologic specimens. If NCI retains ownership of specimens, the contractor shall collect, verify and transfer the requested biologic specimens from the site to a NCI-specified repository or laboratory at NCI's expense.

## **11. REPORTING ADVERSE EVENTS**

**DEFINITION:** AE means any untoward medical occurrence associated with the use of a drug in humans, whether or not considered drug related. An AE can therefore be any unfavorable and unintended sign, symptom, or disease temporally associated with participation in a study, whether or not related to that participation. This includes all deaths that occur while a participant is on a study.

Please note that all abnormal clinical laboratory values that are determined to be of clinical significance based on a physician's assessment are to be reported as AEs. Those labs determined to be of no clinical significance or of unknown clinical significance (per the physician's assessment) should not be reported as AEs. Any lab value of unknown clinical significance should continue to be investigated/followed-up further for a final determination, if possible.

A list of AEs that have occurred or might occur can be found in §6.2 Reported Adverse Events and Potential Risks, as well as the Investigator Brochure or package insert.

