#### 7. Safety and adverse effects of treatment:

Evaluate safety and adverse effects of the treatment by CTCAE 4.0 toxicity scale.

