## 6.2 Reported Adverse Events and Potential Risks

According to the exemestane US prescribing information, treatment-emergent adverse events (TEAEs) more commonly reported by EBC patients treated with exemestane compared with placebo were (in order of frequency): hot flashes (33%), alopecia (15%), hypertension (15%), depression (10%), diarrhea (10%), dermatitis (8%), headache (7%), and myalgia (6%). TEAEs similarly or less commonly reported by EBC patients treated with exemestane compared with placebo were (in order of frequency): arthralgia (29%), increased sweating (18%), insomnia (14%), nausea (12%), fatigue (11%), abdominal pain (11%), dizziness (10%), edema (6%), and anxiety (4%). Elevations of alkaline phosphatase (14–15%), bilirubin (5–7%), and creatinine (6%) were more commonly seen in patients receiving exemestane than tamoxifen or placebo. Though rare, cardiac ischemic events (myocardial infarction, angina, and myocardial ischemia) were elevated in EBC patients treated with exemestane (1.6%) compared with tamoxifen (0.6%).

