#### **7.6 Final Study Visit – Day of Surgery**

The surgical procedure will be standard of care and not altered based on participation.

The following research procedures will occur prior to surgery:

- Physical exam with vitals including height, weight and body mass index
- Medical/ surgical history review and update
- Review of concomitant medications and adverse events.
- Laboratory tests will include CBC with a differential, CMP, estradiol and progesterone.
- Appendix E: follow-up tobacco and alcohol assessment questionnaires will be administered.
- The vaginal tampon, which was placed by the participant 8-12 hours before surgery will be removed in the operating room by the surgeon prior to the surgical procedure. Attempt should be made to obtain tampon specimen at day of surgery visit even if baseline sample was not obtained.
- Research blood sample to obtain plasma pharmacokinetics of exemestane

At the time of surgery, once the patient is under anesthesia the vaginal tampon will be removed and processed in the same way as the pre-treatment tampon. The tampon will be processed at each institution and the resultant cells and washings will be frozen and shipped on dry ice to the University of Minnesota for DNA and protein extraction per section 10.2.

The surgical pathologic specimen (the uterus) will be processed as is the usual standard at each institution. A portion of the FFPE tumor block will be collected and batch shipped to UMN at the end of the study to be cut into 10 unstained 5 $\mu$ m slides. If the FFPE block cannot be sent due to limited amount of tumor, then 10 unstained 5 $\mu$ m slides will be cut and the slides will be shipped to UMN. An additional section of the tumor, up to 1x1x1cm, will be collected after removal of the uterus or from the pathology lab, cut in half and snap frozen as per institutional policy for genetic and protein analysis. If there is not a visible lesion, select a random 1x1x1 cm from the endometrium, or smaller if the pathology team needs to review more of the endometrium. This is done at the investigators clinical discretion. This tumor section will also be batch shipped to UMN at the end of the study. The tumor biopsy specimens, the FFPE blocks and the

unstained slides will be sent to the University of Minnesota (UMN) for proteomics, DNA analysis, histologic review, and IHC.

The study coordinator or designee will collect the exemestane supply and completed drug log.

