### **13.7 Evaluation of Toxicity**

All participants will be evaluable for toxicity from the time of their first dose of exemestane using CTCAE version 4.0. The incidence and severity of adverse events will be summarized with frequency and proportion.

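### Laboratory abnormalities reach the CTCAE safety summary only through an undefined physician judgement, so low-grade rises may be under-reported by an unknown amount

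*Combined protocol and SAP*

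**What the plan says.** Secondary objective 7 (section 1.2, repeated in 8.2.6) is: "Evaluate safety and adverse effects of the treatment by CTCAE 4.0 toxicity scale". The analysis is in section 13.7: "The incidence and severity of adverse events will be summarized with frequency and proportion". Section 13.6 puts every woman who took any exemestane into the toxicity analysis.

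Section 11 sets the entry rule for laboratory findings. On one side, "all abnormal clinical laboratory values that are determined to be of clinical significance based on a physician's assessment are to be reported as AEs". On the other, "Those labs determined to be of no clinical significance or of unknown clinical significance (per the physician's assessment) should not be reported as AEs". It then adds: "Any lab value of unknown clinical significance should continue to be investigated/followed-up further for a final determination, if possible". No threshold or guidance for clinical significance is given.

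Section 6.2 names the laboratory effects known for the drug: "Elevations of alkaline phosphatase (14–15%), bilirubin (5–7%), and creatinine (6%) were more commonly seen", the comparison being with tamoxifen or placebo. For the day of surgery, section 7.6 states: "Laboratory tests will include CBC with a differential, CMP, estradiol and progesterone". Sections 3 and 7.3 schedule the same two panels at baseline. The footnotes to section 7.1 show that the metabolic panel contains alkaline phosphatase, total bilirubin and creatinine.

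**The concern.** The endpoint is defined on a graded toxicity scale, but what enters it is decided by a separate judgement about clinical importance. The two do not match at the low end. The general severity table in 11.1.3 describes grade 1 as covering asymptomatic findings, seen on testing alone, that need no intervention. A physician may reasonably regard such a finding as not clinically significant, and section 11 then keeps it out of the adverse event data.

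The laboratory effects that section 6.2 leads one to expect could be of this kind. If they are filtered out, the planned table shows a low count, and a reader of that table cannot separate few rises from few rises judged important. Section 2 describes the need as a treatment with few side effects and raises chemopreventive use, so low-grade laboratory changes are relevant to whoever plans the next study.

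**Working it through.** The plan states no figure for laboratory toxicity, so there is nothing to reproduce. The check has two parts: tracing a laboratory value through the plan, and putting a range on the possible shortfall.

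**Tracing a raised value**

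1. It is measured at baseline and, if the woman reaches the surgical visit, on the day of surgery (sections 3, 7.3, 7.6). No other on-treatment panel is scheduled.
2. It becomes an adverse event only on a physician's judgement of clinical significance (section 11). Section 11.1.5 applies the same test to follow-up of laboratory abnormalities.
3. Only adverse events are tabulated (13.7). No part of section 13 uses CBC or metabolic panel values directly: there is no grading from the number, shift from baseline or mean change.
4. A value of unknown significance is to be followed up where possible. But adverse event recording stops when surgery begins (11.1.1). Apart from the Italian site, post-operative contact is made only for unresolved adverse events attributed to the agent (7.7 and footnote 1 of 7.1), and a value of unknown significance is not yet an adverse event. The Italian site sees every woman post-operatively, but 7.7 describes no repeat panel there.
5. Section 4.1.6 admits women with total bilirubin or creatinine up to 1.5 times the upper limit of normal, and sets no limit for alkaline phosphatase. A surgery-day value therefore has to be read against that woman's baseline.

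**Size**

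Inputs: N = 40 (the maximum enrolment in 13.1) and the rates p in 6.2. The share f of rises that a physician would call clinically significant is not given, so it is an assumption with range 0 to 100%.

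Expected rises = N × p:

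- alkaline phosphatase: 40 × 0.14 to 0.15 = 5.6 to 6.0
- bilirubin: 40 × 0.05 to 0.07 = 2.0 to 2.8
- creatinine: 40 × 0.06 = 2.4
- total: 10.0 to 11.2 analyte-level rises (a woman can count more than once)

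Expected reported rises = N × p × f, summed over the three analytes. The last column is the chance that at least one bilirubin rise is reported, 1 − (1 − p × f)^40.

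| Assumed f | Rises reported | P(at least one bilirubin rise) |
|---|---|---|
| 0% | 0 | 0 |
| 10% | 1.0 to 1.1 | 0.182 to 0.245 |
| 25% | 2.5 to 2.8 | 0.395 to 0.506 |
| 50% | 5.0 to 5.6 | 0.637 to 0.760 |
| 75% | 7.5 to 8.4 | 0.783 to 0.884 |
| 100% | 10.0 to 11.2 | 0.871 to 0.945 |

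More than half of the rises are lost only if f is below 50%.

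The rates come from early breast cancer patients, and dosing here lasts 21 to 42 days. If short exposure produced one third of those rates (an assumption, for illustration), the total would be 10.0/3 to 11.2/3 = 3.3 to 3.7 rises before any filtering.

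**The case against.** The strongest case against is that this is an unspecified descriptive table in a small single-arm pilot whose primary question is Ki-67. Section 13.7 does not forbid a laboratory summary. The filter governs adverse event entry and destroys no measurements. Higher-grade rises would probably pass it, and section 5.6 separately acts on related events of grade 3 or above. The monitoring committee reviews study data periodically (12.4, 13.9). With no concurrent control, a handful of mild rises could not be attributed to the drug in any case.

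Much of this stands, and it rules out several stronger readings that a reader might infer:

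- **That the listed rises will be largely missing, or the reported rate near zero.** The documents give no share judged significant; the loss could be none or all.
- **That a true absence could never be told from a filtered one.** The planned table alone cannot tell them apart, but the scheduled panel values could.
- **That liver enzymes in general are affected.** Section 6.2 lists alkaline phosphatase; it lists no AST or ALT rise.
- **That every woman will have two panels.** That is the schedule. Women who withdraw or do not reach surgery may lack the second.
- **That lack of blinding biases the comparison.** There is one treated arm, so no difference between arms can be created this way.

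What the objection does not remove is the mismatch between a graded safety endpoint and an intake rule that can drop its lowest grade, with no value-based analysis planned to compensate. The follow-up clause helps little, given when the only on-treatment panel is drawn.

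**Conclusion.** The concern holds in a limited form. Low-grade, asymptomatic laboratory rises may be under-counted in the CTCAE summary, and the plan gives no means of saying by how much. At the section 6.2 rates and 40 treated women, the shortfall lies between 0 and about 10.0 to 11.2 analyte-level rises.

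That range assumes full enrolment and rates carried over from another disease setting. Fewer treated women or a smaller short-term effect would shrink it in proportion. That the lost rises would mainly be mild is a plausible inference, not something the documents state. The point affects a secondary, descriptive endpoint and leaves the primary analysis untouched. It is a worthwhile, inexpensive improvement rather than a flaw in the design.

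**What to change.** Leave the adverse event reporting rule in section 11 as it is. Add to section 13.7:

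- All available CBC and metabolic panel values at baseline and on the day of surgery are graded by CTCAE v4.0 from the numeric result and the site's normal range, without regard to clinical significance.
- Results are presented as a baseline-to-surgery grade shift table for each analyte, with the mean change in alkaline phosphatase, bilirubin and creatinine.
- The population is all women who took any exemestane, stating how many have both panels.
- The table is descriptive and, without a concurrent control, does not attribute changes to the drug.

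The tests are already scheduled, and section 14.2.3 already requires laboratory normal ranges, so no visit, sample or participant is added. The database specification referred to in section 12.2 is not among the documents; confirm that it holds the numeric values and ranges. If it does, the cost is one programmed table. The other consequence is that the reported laboratory toxicity rate may look less favourable.

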### **11.1 Adverse Events**

#### **11.1.1 Reportable AEs**

All AEs that occur after the informed consent is signed and baseline assessments are completed (including run-in) must be recorded on the AE CRF (paper and/or electronic) whether or not related to study agent and stop at the beginning of surgery. EOG site must also record on the AE CRF all the AEs that occur after the pre-screening informed consent is signed and screening assessments are completed.

All SAEs, including all hospitalizations, during the study period will be reported as per DCP SAE reporting procedures, with the following exception:

- i. Hospitalization for planned surgery will not be reported. However, if this hospitalization event lasts longer than the usual period at the institution (as determined by the Site Principal Investigator or Sponsor), it will be reportable as an SAE. Adverse events (AEs) relevant to the prolongation of this hospitalization will also be collected and reported on AE CRFs.

#### **11.1.2 AE Data Elements:**

The following data elements are required for AE reporting.

- AE verbatim term
- NCI Common Terminology Criteria for Adverse Events version 4.0 (CTCAE v4.0) AE term (MedDRA lowest level term)
- CTCAE (MedDRA) System Organ Class (SOC)
- Event onset date and event ended date
- Treatment assignment code (TAC) at time of AE onset
- Severity grade
- Attribution to study agent (relatedness)
- Whether or not the event was reported as a SAE
- Whether or not the subject dropped due to the event
- Outcome of the event

### 11.1.3 Severity of AEs

11.1.3.1 Identify the AE using the CTCAE version 4.0. The CTCAE provides descriptive terminology (MedDRA lowest level term) and a grading scale for each AE listed. A copy of the CTCAE can be found at [http://ctep.cancer.gov/protocolDevelopment/electronic\\_applications/ctc.htm](http://ctep.cancer.gov/protocolDevelopment/electronic_applications/ctc.htm)

AEs will be assessed according to the grade associated with the CTCAE term. AEs that do not have a corresponding CTCAE term will be assessed according to the general guidelines for grading used in the CTCAE v4.0. as stated below.

#### **CTCAE v4.0 general severity guidelines:**

Grade	Severity	Description
1	Mild	Mild; asymptomatic or mild symptoms; clinical or diagnostic observations only; intervention not indicated.
2	Moderate	Moderate; minimal, local or noninvasive intervention indicated; limiting age-appropriate instrumental activities of daily living (ADL)*.
3	Severe	Severe or medically significant but not immediately life-threatening; hospitalization or prolongation of hospitalization indicated; disabling; limiting self-care ADL**.
4	Life-threatening	Life-threatening consequences; urgent intervention indicated.
5	Fatal	Death related to AE.

#### **ADL**

\*Instrumental ADL refers to preparing meals, shopping for groceries or clothes, using the telephone, managing money, *etc.*

\*\*Self-care ADL refers to bathing, dressing and undressing, feeding self, using the toilet, taking medications, and not bedridden.

### 11.1.4 Assessment of relationship of AE to treatment

The possibility that the AE is related to study agent will be classified as one of the following: not related, unlikely, possible, probable, and definite.

### 11.1.5 Follow-up of AEs

All AEs, including lab abnormalities that in the opinion of the investigator are clinically significant, will be followed according to good medical practices and documented as such.

## **11.2 Serious Adverse Events**

11.2.1 DEFINITION: Regulations at 21 CFR §312.32 (revised April 1, 2014) defines an SAE as any untoward medical occurrence that at any dose has one or more of the following outcomes:

- Death
- A life-threatening AE
- Inpatient hospitalization or prolongation of existing hospitalization

- A persistent or significant incapacity or substantial disruption of the ability to perform normal life functions
- A congenital anomaly or birth defect
- Important medical events that may not be immediately life-threatening or result in death or hospitalization should also be considered serious when, based upon appropriate medical judgment, they may jeopardize the patient and may require intervention to prevent one of the other outcomes.

#### 11.2.2 Reporting SAEs to DCP

11.2.2.1 The Lead Organization and all Participating Organizations will report SAEs on the DCP SAE Report Form found at <http://prevention.cancer.gov/clinical-trials/clinical-trials-management/protocol-information-office/pio-instructions-and-tools/2012-consortia>.

11.2.2.2 Contact the DCP Medical Monitor by phone or email (email preferable) within 24 hours of knowledge of the event.

[name]  
Chief, Lung & Upper Aerodigestive Cancer Research Group  
NCI/Division of Cancer Prevention  
[name]  
[name]  
[contact]  
[contact]  
email: [[contact]](mailto:[contact])

Include the following information when calling the Medical Monitor:

- Date and time of the SAE
- Date and time of the SAE report
- Name of reporter
- Call back phone number
- Affiliation/Institution conducting the study
- DCP protocol number
- Title of protocol
- Description of the SAE, including attribution to drug

11.2.2.3 The Lead Organization and all Participating Organizations will email written SAE reports to DCP's Regulatory Contractor CCS Associates, Inc. (CCSA; [contact]) at [[contact]](mailto:[contact]) as well as DCP medical monitor simultaneously within 48 hours of learning of the event using the fillable PDF SAE Report Form.

11.2.2.4 The DCP Medical Monitor and CCSA regulatory and safety staff will determine which SAEs require FDA submission as IND safety reports.

11.2.2.5 The Lead Organization and all Participating Organizations will comply with applicable regulatory requirements related to reporting SAEs to the IRB/IEC.

#### 11.2.3 Follow-up of SAE

Site staff should send follow-up reports as requested when additional information is available. Additional information should be entered on the DCP SAE Report Form in the appropriate format. Follow-up information should be sent to DCP as soon as available. Any SAE will be followed-up until resolution as per the GCP practice.

### **11.3 Suspected Unexpected Serious Adverse Reaction**

An adverse event or suspected adverse reaction is considered by the sponsor and/or study investigator as being unexpected, serious and as having a reasonable possibility of a causal relationship with the study drug. At EOG site, in case of SUSAR (Suspected Unexpected Serious Adverse Reaction) the Pharmacovigilance Unit performs the regulatory notification to EudraVigilance and to the local EC in order to comply with the current European regulatory requirements.

## **12. STUDY MONITORING**

### **12.1 Data Management**

All of the procedures outlined in the University of Wisconsin Chemoprevention Consortium standardized Data Management Plan (approved 09/23/2019) will be followed in this protocol. Please refer to this document for additional details on data management procedures. The University of Wisconsin Carbone Cancer Center's OnCore database will be the database of record for the protocol and subject to NCI and FDA audit. OnCore is a web-based clinical trials database. Data entry will be performed by the CLO where staff is trained in OnCore and applicable regulatory requirements such as 21 CFR: Part 11. Data from the OnCore database will be transferred to Federal Security Compliant formats for transmission to DCP according to pre-established DCP standards and procedures.

### **12.2 Case Report Forms**

In lieu of a CRF set, a System Variable Attribute Report (SVAR) will be used to document all questions and data elements to be collected in the database for this protocol. The NCI/DCP approved SVAR will be used to create the electronic data entry pages in the OnCore database. Amendments to the SVAR will be submitted to the DCP Protocol Information Office for review and approval. Data will be extracted from source documents submitted by the PO.

